4.3 Trial Management System

Upon receipt, returned CRFs will be checked manually for inconsistencies and missing data, which will be resolved with ComBAT RAs where possible. Automated electronic checks according to comprehensive data validation plans for each CRF included checks for completeness, internal consistency as well as appropriate data formatting and range checks will be undertaken. Copies of the validation plans are held by data management and the study statistician. Violations of the validation rules will be queried with the RAs and sites as required. All violations and any resulting changes to the data will be documented in an error log file for each CRF, and data fields for which error log entries exist will be completed as '555' or another error code as advised by the data management team in the data.

At the end of the trial, all CRF data, error logs and relevant management database data will be handed over to the trial statistician. The statistician will merge the data and conduct further data checks including checking for consistency of data across questionnaires. Any queries and resulting changes will be processed between the soft and hard lock of the data. The statistician will generate any necessary derived variables in the statistical master data set. Any further data changes and assumptions made to the hard locked data will be documented on a Trial Assumptions Form.

4.4 Location of Data and Associated Files

Data and documents relevant to the statistical analysis will be kept electronically in a folder on the Y Drive (Y:\ Project -- comBAT - Statistics).

5. Analysis

5.1 Analysis Principles

5.1.1 General Principles

Data will be analysed and reported in accordance with CONSORT guidelines. All analyses will be conducted following the principle of intention-to-treat unless stated otherwise. Statistical tests will be two-sided at the 5% significance level. Estimates of group differences will be presented with 95% confidence intervals.

5.2 Scoring of Questionnaire Data

The following sections outline how the participant completed questionnaires will be scored and state any methods used for dealing with missing data, if necessary. Copies of all questionnaires are provided in the Appendix (Section 8.2).

5.2.1 RCADS-25

The 25 items of the RCADS questionnaire are scored from 0-3. The 25 items are split into two sub-scales: anxiety scale (15 items) and depression scale (10 items). The raw scores for each sub-scale will be calculated and then an overall score will be calculated.

The total raw scores and overall raw score will be converted into T-scores (further details of conversions in Section 5.3.1 below). Higher t-scores denote greater clinical need. The t-scores will be arranged into the following clinical cut-offs: 0-64 non-clinical range, 65-69 borderline clinical range, and ≥ 70 clinical range.

For missing data, mean imputation will be used when at most three items are missing from the anxiety sub-scale and at most two items are missing for the depression sub-scale. If the child's date of birth/age is missing and/or the child's sex is missing, selected as 'Non-binary' or 'Prefer not to say', the RCADS-25 T-Score cannot be calculated.

Guidance for calculating T-scores and missing data refers to the RCADS-25 Child Version Scoring Program 3.1 (Ebesutani et al (2012)).

5.2.2 PHQ-9A

The PHQ-9A consists of 9-items with each item scoring from 1-5. The total score will be calculated, with higher scores demonstrating greater levels of depression. The 4 supplementary items referring to the 'at-risk' level of the young person will be scored individually and separate from the first 9-items.

If at least 3-items are not scored or are missing, then the total PHQ-9A score will not be calculated. For 1-2 missing items, a pro-rata score will be calculated based on the remaining completed items.

5.2.3 CDRS-R

The CDRS-R has 3 sub-scales containing 17 items overall. Items 4, 5 and 16 are scored from 1-5 and the remaining items are scored from 1-7. The raw scores for each sub-scale will be calculated and then an overall score will be calculated.

The overall raw scores will range from 17 to 113. These overall raw scores will be converted to corresponding T-scores as displayed on the questionnaire. The lower the T-score the less

likely for a depressive disorder diagnosis is to be made. The CDRS T-scores will be grouped into three categories, using a cut-off score of 54 and 64, such that a T-score of ≤ 54 is interpreted such that a depressive disorder is unlikely to be confirmed in any further evaluation, score of 55-64 suggests depression is possible to be diagnosed after further comprehensive testing (emerging depression) and scores >65 indicate likely depression.

Items 15 and 17 require the researcher to rate the child's facial expressions and body movement during the follow-up. The appointment may be via telephone or online (with no camera) which in these situations, the researcher would be unable to score these items. Only questionnaires with all items completed will be included in the secondary analysis model, however these participants will be included in a sensitivity analysis detailed in section 5.9.2.1.

Further information of the interpretation of the T-score for the CDRS-R can be found in the Appendix (section 8.2.2).

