5.2.4 BADS-SF

The BADS-SF consists of 9 items that are scored from 0-6 and split across two sub-scales. For each item the greater the score suggests higher behavioural activation except for items 1, 6, 7 and 8 whereby the scoring is reversed. The total score ranges from 0-54 with the reversed scores considered e.g., a score of 0 would be included in the calculation as a 6, 1 as a 5 and so on.

There is no guidance for the BADS-SF regarding scoring questionnaires with missing items. Here we use the rule where the missing items of a Patient Reported Outcome Measure (PROM) should only be replaced with the means of the non-missing items to facilitate the calculation of a score, if the number of non-missing items is less than 10% of the total number of items in the PROM. In this case, mean imputation will be used if one item is missing in the BADS-SF and unable to be scored if more than one item is missing.

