5.3 Derivation of Variables and Outcomes

5.3.1 RCADS T-scores

The RCADS T-scores are derived by transforming the raw scores depending on sex and the grade they are in at school. As UK schools do not use grades, the young person's age will be used to approximate their school grade. This will be approximated by adding 6 to the young person's age as suggested by the RCADS-25 Child Version Scoring Resources (Ebesutani et al (2012)). Table 2 shows the specific transformations for each permutation of sex and age.

Table 2: RCADS raw score transformations to derive T-scores for each sub-scale and overall.

Sex	Age (Grade)	Depression T-score	Anxiety T-score	Overall T-score
Male	10 (4)	$((Score - 9.90)*10)/4.93 + 50$	$((Score - 15.19)*10)/7.09 + 50$	$((Score - 25.10)*10)/11.10 + 50$
	11-12 (5-6)	$((Score - 7.13) *10)/4.22 + 50$	$((Score - 11.63)*10)/6.45 + 50$	$((Score - 18.76)*10)/9.38 + 50$
	13-14 (7-8)	$((Score - 7.56) *10)/3.75 + 50$	$((Score - 10.48)*10)/5.36 + 50$	$((Score - 18.04)*10)/7.92 + 50$
	15-16 (9-10)	$((Score - 7.50) *10)/4.18 + 50$	$((Score - 9.70)*10)/5.45 + 50$	$((Score - 17.20)*10)/8.53 + 50$
	17-18 (11-12)	$((Score - 7.64) *10)/4.37 + 50$	$((Score - 9.96)*10)/4.32 + 50$	$((Score - 17.60)*10)/7.24 + 50$
Female	10 (4)	$((Score - 9.68)*10)/4.97 + 50$	$((Score - 16.25)*10)/8.42 + 50$	$((Score - 25.93)*10)/12.24 + 50$
	11-12 (5-6)	$((Score - 8.03)*10)/5.00 + 50$	$((Score - 13.49)*10)/7.62 + 50$	$((Score - 21.53)*10)/11.73 + 50$
	13-14 (7-8)	$((Score - 8.08)*10)/4.34 + 50$	$((Score - 12.74)*10)/6.22 + 50$	$((Score - 20.82)*10)/9.46 + 50$
	15-16 (9-10)	$((Score - 8.14)*10)/4.37 + 50$	$((Score - 11.31)*10)/5.33 + 50$	$((Score - 19.45)*10)/8.63 + 50$
	17-18 (11-12)	$((Score - 8.59)*10)/3.67 + 50$	$((Score - 11.50)*10)/5.34 + 50$	$((Score - 20.09)*10)/7.79 + 50$

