5.9.2.1 Sensitivity analysis for non-visual appointments

A sensitivity analysis will be conducted including the participant's CDRS-R T-scores that were unable to complete Items 15 or 17 due to being a telephone or online (with no camera) appointment. The secondary CDRS-R analysis models (described above in section 5.9.2) will be rerun but including the participants that had these types of appointments.

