	55-64	It is possible that a depressive disorder might be confirmed in a comprehensive diagnostic evaluation. Further evaluation should be pursued if any of the following conditions are applicable: 
 • Moderate to severe ratings were made in any symptom areas • The rating for Suicidal Ideation is 3 or above • A chronic course (i.e., more than one year) is described for a clinically significant indicator of depressive mood (i.e., Difficulty Having Fun, Depressed Feelings, Depressed Facial Affect, or Irritability) 																																																																																																																																																																																																																																											
	65-74	A depressive disorder is likely to be confirmed in a comprehensive diagnostic evaluation. Further evaluation should be pursued.																																																																																																																																																																																																																																											
	75-84	A depressive disorder is very likely to be confirmed. Further evaluation should be pursued.																																																																																																																																																																																																																																											
	85 or higher	A depressive disorder is almost certain to be confirmed. Intervene and evaluate immediately.																																																																																																																																																																																																																																											
Comparison of Symptom Ratings from All Sources																																																																																																																																																																																																																																													

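### CDRS-R and RCADS-25 category rules leave T-scores unclassified, and the non-visual CDRS-R sensitivity analysis has no scoring rule for unrated items

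*SAP*

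**What the plan says.** **CDRS-R groups.** Section 5.2.3 forms three T-score groups "using a cut-off score of 54 and 64". The lowest is 54 or below. For the middle group, "score of 55-64 suggests depression is possible to be diagnosed". For the top group, "scores >65 indicate likely depression". On the form in appendix 8.2.2, the 65-74 band reads "A depressive disorder is likely to be confirmed in a comprehensive diagnostic evaluation". The groups feed the ordinal model in 5.9.2 and Table 7.

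**RCADS-25 groups.** Section 5.2.1 gives "0-64 non-clinical range, 65-69 borderline clinical range", with 70 and above as clinical. Table 2 in 5.3.1 derives T by a linear formula with two-decimal constants. The groups feed the ordinal model in 5.9.1 and Table 7.

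**Non-visual CDRS-R interviews.** Section 5.2.3 says items 15 and 17 cannot be rated by telephone or with the camera off, and keeps incomplete forms out of the main CDRS-R models. Section 5.9.2.1 then reruns those models "including the participant's CDRS-R T-scores that were unable to complete Items 15 or 17". The only T conversion in the SAP is the look-up on the 17-item raw total, 17 to 113.

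**Two wording points.** On school grade, section 5.3.1 says "This will be approximated by adding 6 to the young person's age". Section 5.2.4 allows item-mean replacement on the BADS-SF "if the number of non-missing items is less than 10% of the total number of items in the PROM", and then states that one missing item is imputed and more than one makes the score unobtainable.

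**The concern.** A category rule should place every possible score in exactly one group. Two rules here do not, and they define the responses of prespecified ordinal models. Someone coding them literally gets a missing category. Anyone else must choose a convention the SAP does not state, and that choice should be fixed before the data are seen.

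The sensitivity analysis in 5.9.2.1 exists to show what happens when non-visual interviews are added. It cannot be run uniquely unless the SAP says how a form with one or two unrated items becomes a T-score.

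**Working it through.** **1. CDRS-R groups.** The rules are T <= 54, 55 <= T <= 64 and T > 65. Testing each whole number from 50 to 69, only T = 65 meets none of them. With a cut-off of 64 the top group would begin at 65, which is also where the form's band begins. The two sources agree with each other and disagree with the written rule.

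**2. RCADS-25 groups.** Table 2 gives T = (raw - m) x 10 / s + 50. I took the overall-score constants, applied them to every whole raw score from 0 to 75 for ages 11-18, and listed T strictly between 64 and 65 or between 69 and 70.

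| Sex, age | m | s | Raw score (T) in a gap |
|---|---|---|---|
| Male 11-12 | 18.76 | 9.38 | 32 (64.12), 37 (69.45) |
| Male 13-14 | 18.04 | 7.92 | none |
| Male 15-16 | 17.20 | 8.53 | 34 (69.70) |
| Male 17-18 | 17.60 | 7.24 | 28 (64.36), 32 (69.89) |
| Female 11-12 | 21.53 | 11.73 | 38 (64.04), 39 (64.89), 44 (69.16) |
| Female 13-14 | 20.82 | 9.46 | 35 (64.99), 39 (69.22) |
| Female 15-16 | 19.45 | 8.63 | 32 (64.54), 36 (69.18) |
| Female 17-18 | 20.09 | 7.79 | 31 (64.01), 35 (69.14) |

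Example, female 15-16, raw 32: (32 - 19.45) x 10 / 8.63 + 50 = 64.54.

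The count is 2 + 0 + 1 + 2 + 3 + 2 + 2 + 2 = 14 raw scores, in seven of eight bands. Truncating puts all 14 in the lower group. Rounding moves up those with a decimal part of at least 0.5: 69.70, 69.89, 64.89, 64.99 and 64.54. That is five.

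**3. CDRS-R with unrated items.** The SAP's own range reproduces: the minimum is 17 x 1 = 17 and the maximum is 3 x 5 + 14 x 7 = 113. Items 15 and 17 are each scored 1-7. Without both, the sum runs from 15 to 3 x 5 + 12 x 7 = 99. If unrated items were omitted and nothing put in their place, the total would be short by 1 to 7 points for one item and by 2 to 14 for both, always towards less depression. Sections 5.2.1, 5.2.2 and 5.2.4 give missing-item rules for the RCADS-25, PHQ-9A and BADS-SF. Section 5.2.3 gives none for the CDRS-R beyond exclusion from the main models.

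**4. Grade.** Adding 6 turns ages 12-18 into grades 18-24, but Table 2 holds grades 4-12. Subtracting 6 gives grades 6-12 and matches (age 10 is paired with grade 4).

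**5. BADS-SF.** Ten per cent of 9 items is 0.9. Read literally, the condition is met only when no item is answered. Read as referring to missing items, one of nine is 1/9 = 11.1%, which still exceeds 10%. Correcting the one word therefore does not make the stated threshold support the one-item allowance.

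**The case against.** The intent behind the CDRS-R groups can be recovered: the same sentence gives a cut-off of 64, and the form's band starts at 65. It is also not certain that anyone can score exactly 65. The look-up is damaged in the copy reviewed, its legible part ends at T = 63, and it skips values. Both points stand. They limit the likely reach but do not make the written rule correct.

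For the RCADS-25, any rounding convention places every score, so it is too much to say participants would be lost. Section 5.2.1 also defers T-score calculation to an external scoring program, which may fix the rounding. That stands too. But the SAP states no convention, and the choice matters for five raw scores.

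A reader might infer from 5.9.2.1 that unadjusted 15-item sums will be put through the 17-item look-up. The SAP does not say so. It gives no scoring rule at all, so the 1-7 and 2-14 point shortfalls are conditional on omission without adjustment. A reader might also infer a spurious difference between arms. That would need appointment mode to differ by arm, and nothing in the SAP indicates that it will.

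The grade and BADS-SF slips might look like scoring errors, the first in the primary outcome. They are not. Table 2 is indexed by age directly, and the one-item BADS-SF rule is stated outright.

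**Conclusion.** The point holds in three limited parts.

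- The CDRS-R rule leaves T = 65 unclassified, against the SAP's own cut-off and its appendix. Whether any raw score converts to 65 is unconfirmed.
- The RCADS-25 rule leaves 14 overall raw scores in seven of eight sex-by-age bands between groups, five of them sensitive to rounding. This assumes whole raw scores and that the overall T-score is the one grouped in 5.9.1.
- Section 5.9.2.1 lacks a scoring rule for unrated items 15 and 17.

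The first two reach only the ordinal secondary analyses. The third reaches only a sensitivity analysis of a secondary outcome. The primary analysis uses the continuous RCADS-25 T-score and is not affected. The slips in 5.3.1 and 5.2.4 are editorial.

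**What to change.** - **5.2.3:** write the top CDRS-R group as T >= 65.
- **5.2.1:** define the RCADS-25 groups as <65, 65 to <70 and >=70 on the unrounded T-score. For the scores in the table this gives the same result as truncating.
- **5.9.2.1:** state that an unadjusted short sum is not converted to a T-score, and choose one route.
  - Pro-rate or impute the unrated items before conversion. The SAP already pro-rates the PHQ-9A. A pro-rated total is often not a whole number, so say how it is rounded before the look-up.
  - Alternatively, analyse the 15-item sum for everyone at all visits, baseline included, and rerun the complete-form sample on that sum so the two results share a scale. The downside is that the T-score groups do not apply to this sum, so the ordinal model could not be repeated.
- **5.3.1:** change adding 6 to subtracting 6.
- **5.2.4:** replace the percentage rationale with a plain rule of at most one of nine items missing, the mean being taken after items 1, 6, 7 and 8 are reversed.

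The cost is SAP wording and at most one extra derived score.

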5.9.2 CDRS-R

The CDRS-R will be analysed first using the T-scores as a continuous measure and second as an ordered categorical measure.

The continuous CDRS-R T-scores will be used as the response variable. This analysis will compare the adjusted mean difference of the CDRS-R score between treatment arms at both 6- and 12-months post randomisation. A linear mixed effects regression model will be used, replacing the baseline value of RCADS-25 T-Score to that of the baseline CDRS-R T-score, with all other fixed and random covariates remaining the same as the primary model.

For the second analysis, the CDRS-R T-scores will be categorised into three groups as defined in section 5.2.3. This analysis will compare the odds of being in a higher category than the non-diagnosable depression category for each treatment arm. A mixed ordinal logistic regression model will be used, replacing the baseline value of RCADS-25 T-Score to that of the baseline CDRS-R T-score, with all other fixed and random covariates remaining the same as the primary model. This will be analysed at both 6- and 12-months post randomisation. The proportional odds assumption for ordinal regression models will be assessed using the Brant test.

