8.1.2 Demographics and Baseline Characteristics

Table 3: Demographic and baseline characteristics presented by treatment allocation for the 'as randomised' and 'as analysed' participants

	As randomised (n=)		As analysed (n=)	
	Behavioural Activation (n=)	Usual Care (n=)	Behavioural Activation (n=)	Usual Care (n=)
Age, n (%) n (%) Mean (SD) Median (IQR) Min, Max				
Gender, n (%) Male Female Non-binary Prefer not to say Missing				
Ethnicity, n (%) English/Welsh/Scottish/Northern Irish/ British Irish Gypsy or Irish Traveller Any other White background Indian Pakistani Bangladeshi Chinese Any other Asian background White and Black Caribbean White and Black African White and Asian Any other mixed/multiple ethnic background African Caribbean Any other Black / African / Caribbean background Arab Any other ethnic group Prefer not to say Missing				
Religion, n (%) Protestant (Church of England) Catholic Mormon Jehovah's Witness Orthodox Other Christian Atheist Agnostic Jewish Muslim Buddhist Hindu Other World Religion Prefer not to say Other				

	As randomised (n=)		As analysed (n=)	
	Behavioural Activation (n=)	Usual Care (n=)	Behavioural Activation (n=)	Usual Care (n=)
Missing				
Currently living with, n (%)				
Biological Parent(s)				
Adoptive Parent(s)				
Foster Carer(s)				
Children's home				
Partner				
Friend				
Alone				
Other				
Missing				
Education, n (%)				
Secondary				
Further/Higher (University or College)				
Not in education				
Other				
Missing				
Employment, n (%)				
Employed Full-Time				
Employed Part-Time				
Self Employed				
Unemployed				
Seasonal Holiday Job				
Volunteering				
Other				
Missing				

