Depressed Facial Affect	1 2 3 4 5 6 7	1 2 3 4 5 6 7	1 2 3 4 5 6 7	1 2 3 4 5 6 7	1 2 3 4 5 6 7	1 2 3 4 5 6 7	1 2 3 4 5 6 7	1 2 3 4 5 6 7	1 2 3 4 5 6 7	1 2 3 4 5 6 7	1 2 3 4 5 6 7	1 2 3 4 5 6 7																																																																																																																																																																																																																																	
Listless Speech	1 2 3 4 5	1 2 3 4 5	1 2 3 4 5	1 2 3 4 5	1 2 3 4 5	1 2 3 4 5	1 2 3 4 5	1 2 3 4 5	1 2 3 4 5	1 2 3 4 5	1 2 3 4 5	1 2 3 4 5	1 2 3 4 5																																																																																																																																																																																																																																
Hypoactivity	1 2 3 4 5 6 7	1 2 3 4 5 6 7	1 2 3 4 5 6 7	1 2 3 4 5 6 7	1 2 3 4 5 6 7	1 2 3 4 5 6 7	1 2 3 4 5 6 7	1 2 3 4 5 6 7	1 2 3 4 5 6 7	1 2 3 4 5 6 7	1 2 3 4 5 6 7	1 2 3 4 5 6 7	1 2 3 4 5 6 7																																																																																																																																																																																																																																

 
 = No apparent difficulties	= Clinically significant difficulties	= Severe clinically significant difficulties	
 
														= No apparent difficulties	= Clinically significant difficulties	= Severe clinically significant difficulties																																																																																																																																																																																																																													
= No apparent difficulties	= Clinically significant difficulties	= Severe clinically significant difficulties																																																																																																																																																																																																																																											

ParticipantID_p7
ID /

Instructions:

Rate each symptom area for this child by writing only one number in the box.
Write *NR* ("Not Rated") in the box if there is insufficient information to derive a rating.

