1. IMPAIRED SCHOOLWORK → CDRS01

Performance is consistent with ability..... **1**
 Decrease in school performance and/or ability to concentrate **2**
 Major interference with performance in most subjects..... **3**
 No motivation to perform **4**
5
6
7

Comment

CDRS01_Info

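### A single unrated CDRS-R item other than 15 or 17 removes the interview from all CDRS-R models in 5.9.2, and neither a scoring rule nor a sensitivity analysis brings it back

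*SAP*

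**What the plan says.** Section 5.2.3 describes the instrument ("The CDRS-R has 3 sub-scales containing 17 items overall") and its total ("The overall raw scores will range from 17 to 113"), which is converted to a T-score by the table on the form. It notes that items 15 and 17 cannot be scored without a view of the participant, and then sets a general rule: "Only questionnaires with all items completed will be included in the secondary analysis model".

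Section 5.9.2.1 relaxes that rule for one group only, participants "unable to complete Items 15 or 17 due to being a telephone or online (with no camera) appointment".

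Section 5.9.2 takes over the primary model, "replacing the baseline value of RCADS-25 T-Score to that of the baseline CDRS-R T-score". A missing baseline score is therefore a missing covariate.

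The form in appendix 8.2.2 tells the rater to enter NR "in the box if there is insufficient information to derive a rating". This applies to every symptom area. Item 1 is about schoolwork, and one of its anchors reads "Decrease in school performance and/or ability to concentrate". Table 3 in 8.1.2 has a baseline row "Not in education", and section 3.4.3 gives the age range as 12 to 18.

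**The concern.** The SAP foresees one reason for an incomplete CDRS-R, the lack of a picture. Its own appendix provides for another, an NR on any item, and the SAP has no rule for that. Sixteen usable ratings out of 17 are then discarded, and no sensitivity analysis shows the effect.

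Two things make this more than a small loss of data. First, an NR at baseline costs both follow-up visits. Second, item 1 gives a foreseeable route by which the loss could depend on education status. The CDRS-R models inherit age, sex, setting and site from the primary model, but not education status. Missingness linked to education would therefore be only partly covered by the missing-at-random assumption that 5.9 carries over.

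The rule is also out of line with the other scales. The RCADS-25 allows up to three anxiety and two depression items to be missing (5.2.1), the PHQ-9A two of nine (5.2.2) and the BADS-SF one of nine (5.2.4).

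**Working it through.** **The plan's own range.** Section 5.2.3 gives three items scored 1-5 (items 4, 5 and 16) and 14 scored 1-7.
- Minimum: 3 × 1 + 14 × 1 = 17.
- Maximum: 3 × 5 + 14 × 7 = 15 + 98 = 113.

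The stated 17 to 113 is reproduced, and it needs all 17 items. With item 1 unrated the sum runs from 16 to 113 − 7 = 106, so the form's raw-to-T conversion cannot be used without a further rule.

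**Following one interview through the rules.** Suppose item 1 is NR and the other 16 items are rated, face to face.
- 5.2.3: not all items are complete, so the interview is out of the 5.9.2 models, continuous and ordinal.
- 5.9.2.1: items 15 and 17 are present, so the interview is not readmitted.
- 5.8.2.1: the multiple imputation is specified for rerunning the primary analysis, so it does not restore the CDRS-R models.

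The same holds for an NR on any of the 15 items 1-14 and 16. At a follow-up visit it costs that visit only. At baseline it leaves the covariate missing and costs both follow-ups.

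**Size.** The SAP gives no NR rate. Assume a proportion p of interviews has one such NR. Expected follow-up from section 3.5 is 236 × (1 − 0.23) = 181.7. If the same people are affected at baseline and follow-up, the loss is p × 181.7.

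| Assumed p | Lost | Left | Power at d = 0.5 |
|---|---|---|---|
| 0 | 0 | 181.7 | 0.911 |
| 2% | 3.6 | 178.1 | 0.905 |
| 5% | 9.1 | 172.6 | 0.896 |
| 10% | 18.2 | 163.5 | 0.880 |

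Power is the normal approximation Φ(0.5 × √(n/2) − 1.96), with n per arm equal to the number left divided by 2 and by the design effect 1.04. For p = 10%, n = 163.5 / 2 / 1.04 = 78.6, 0.5 × √39.3 = 3.134, and Φ(1.174) = 0.880. The effect size and design effect are those set for the RCADS, so the power column is only an illustration for the CDRS-R.

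**If NR were independent between visits,** the 6-month loss would be 1 − (1 − p)²: 4.0%, 9.8% and 19.0%, or about 7, 18 and 35 participants. That does not fit a cause such as education status, which tends to persist, so the table above is the better guide.

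**The case against.** The strongest reply is that the mechanism is permitted but not shown. The form does not tell the rater to mark item 1 NR for someone out of education. It allows NR when information is insufficient, and the anchor quoted above also mentions concentration, which a rater could use. The form refers to a manual that may settle the matter. This stands: the number affected is unknown and could be very small.

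A reader might infer more than the documents support, in three ways.
- That the CDRS-R results would describe mainly those still in school. The share out of education is not given, college students still count as in education, and a follow-up NR costs one visit only. Age is also in the model, which deals with part of any age-related loss.
- That the loss could reach 35 participants. This needs NR to be independent between visits, which contradicts an explanation by education status.
- That the mediation analysis in 5.10.1 suffers in the same way. Its outcome model has no baseline CDRS-R term, so a baseline NR removes nobody there; only a 12-month NR could.

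It can also be said that complete items are a prespecified, conservative requirement for a researcher-rated interview with a fixed conversion table, and that the threshold in 5.2.4 is written for patient-reported measures. That explains some caution. It does not explain why the plan readmits interviews lacking up to two items for one reason and none lacking a single item for any other.

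**Conclusion.** The gap is real and narrow. Read as written, 5.2.3 and 5.9.2.1 together discard any interview with a single NR on items 1-14 or 16, and an NR at baseline discards the participant from 5.9.2 altogether. Under the assumed 2-10% rate, persisting in the same people, about 4-18 of roughly 182 are lost, and illustrative power falls from 0.911 to between 0.905 and 0.880. The loss of precision is small to moderate. Selection by education status is a risk, not a demonstrated bias, and it depends on how raters score item 1. The CDRS-R is a secondary outcome, and the primary RCADS-25 analysis is not affected. The point is worth acting on because the remedy is cheap and is best fixed before the data are seen.

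**What to change.** In 5.2.3, add that where exactly one of items 1-14 or 16 is NR, it is prorated from the participant's other rated items, rescaled to the range of the missing item. For a missing item scored 1 to K, use 1 + (K − 1) × the mean of (x − 1)/(Kx − 1) over the rated items, where x is a rating and Kx the top of that item's range. Round the raw total, then convert to T. If all other items are at their minimum or maximum, the total is 17 or 113, so the conversion table applies. Using all rated items is better than borrowing only from items of the same range, because only items 4, 5 and 16 are scored 1-5.

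Apply the rule at baseline and follow-up. Report the number prorated by arm and education status. Run the CDRS-R models both with these interviews and on strict 17-item completers. At the least, widen 5.9.2.1 to include them. State also what is done when such an NR occurs together with missing items 15 or 17, since 5.9.2.1 does not say how those interviews obtain a T-score.

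The cost is a paragraph in the SAP and a few lines of scoring code. The drawback is that one item in 17 is imputed for a minority of interviews. That is 5.9% of the items, against one in nine (11.1%) already accepted for the BADS-SF.
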